5.2.1. Analyses for Binary Endpoints

5.2.1.1. Cochran-Mantel Haenszel (CMH) Approach

At a single timepoint (eg, IGA response at Week 16 in Part 1 DB), difference in response rate between etrasimod 2 mg QD and placebo groups will be estimated using the Cochran-Mantel Haenszel (CMH) approach adjusting for the stratification factor of IGA score (3 [moderate AD], 4 [severe AD]) at baseline) (Cochran, 1954; Mantel and Haenszel, 1959). Large sample approximation will be used for testing the superiority of etrasimod 2 mg to placebo at Part 1 Week 16 and for forming 95% CI and calculating p-value. This approach will be referred to as CMH. This method is also applicable for all other timepoints in Part 1.

Explicitly, let \hat{p}_{Ai} and \hat{p}_{Bi} represent the estimated response rates for etrasimod 2 mg (A) and placebo (B), respectively, of the i^{th} stratum. Using the CMH weights, the weighted difference in rates between etrasimod 2 mg QD and placebo groups, d, is expressed by:

$$d = \sum_{i} w_i (\hat{p}_{Ai} - \hat{p}_{Bi})$$

where $w_i = \frac{(n_{Ai}n_{Bi})/(n_{Ai}+n_{Bi})}{\sum_i (n_{Ai}n_{Bi})/(n_{Ai}+n_{Bi})}$, is the CMH weight for the i^{th} stratum, with n_{Ai} and n_{Bi}

equal the numbers of participants in the etrasimod and placebo groups, respectively, per stratum. The weights are normalized such that the sum across strata adds up to 1.

Two-sided 95% CI will be estimated using the normal approximation to the binomial distribution via the following method,

$$d \pm \left[z_{1-\alpha/2} \sqrt{var(d)} \right]$$

where the variance of d is $var(d) = \sum_{i} w_i^2 var(\hat{p}_{Ai} - \hat{p}_{Bi})$ with

$$\operatorname{var}(\hat{p}_{Ai} - \hat{p}_{Bi}) = \frac{\hat{p}_{Ai}(1 - \hat{p}_{Ai})}{n_{Ai}} + \frac{\hat{p}_{Bi}(1 - \hat{p}_{Bi})}{n_{Bi}}.$$

Two-sided p-value for the test of the 0 difference between etrasimod 2 mg QD and placebo groups will be calculated as:

$$p=2(1-\Phi(|Z|)),$$

where $\Phi(.)$ is the Gaussian cumulative density function and $Z = \frac{d}{\sqrt{\text{var}(d)}}$ is the Normal Z test statistic.

If there is no (ie, 0%) response or 100% response rate in any one or both of the two treatment groups for the comparison in a stratum, eg, etrasimod vs. placebo, when calculating the proportions above, 0.5 will be added to the number of responses (ie, numerator) and 1 will be

added to the denominator in each treatment in that stratum only corresponding to the pair of comparison for calculating the treatment difference, standard error (ie, $\sqrt{var(d)}$), 95% CI and 2-sided p-value (Agresti, 2002).

When response rate of 0% or 100% is observed in both treatments in comparison and in both strata, no formal comparison will be performed. Estimated response rate of 0% or 100% will be reported as observed. Standard error will be reported as 0. The final results will be expressed in percentages, ie, (proportions x 100)%.

5.2.2. Analyses for Continuous Endpoints

5.2.2.1. Analyses for Continuous Data (Repeated Measures Under Estimand E2)

For a continuous efficacy endpoint analyzed under the Estimand E2 and measured at multiple post-baseline visits (ie, percent change from baseline in EASI score at Week 16), this endpoint will be analyzed using the Jump-to-Control (JTC) method (Carpenter, Roger and Kenward 2013). This JTC method is implemented in the following steps.

- 1. A mixed model for repeated measures (MMRM) that includes fixed effects of treatment group, visit, treatment group-by-visit interaction, actual stratification factor (ie, baseline IGA of 3 or 4 from clinical database), actual-stratification-factor-by-visit interaction, baseline value, and baseline-value-by-visit interaction, will be used to analyze the endpoint's data across all visits (ie, all visits up to Week 16 for Part 1 DB phase). This MMRM will include all relevant observed values across all visits in the pre-intercurrent-event-data without imputation of missing values on the FAS for Estimand E2 (Section 4.1, Appendix 3). The data after intercurrent events of initiation of prohibited medications or discontinuation of study treatment due to any reason will be set to missing (see Appendix 3 for more details on data inclusion). A common unstructured variance-covariance matrix will be used. Estimation of model parameters is performed under the Bayesian framework using MCMC method with non-informative prior densities for the model parameters. This is known as the estimation model.
- 2. Multiple imputation allows for uncertainty of the imputed values. Using the estimated model specified in step 1, missing percent change from baseline value at a particular visit of interest (eg, Week 16) for a participant can be imputed multiple times using multivariate conditional Normal distribution as the imputation model constructed from the parameter values sampled from their posterior densities (using MCMC) conditional on participant's observed values at prior visits, if any.
- 3. In order to apply the JTC concept, for a participant in the etrasimod 2 mg QD group with monotone missing values, the means of the multivariate conditional Normal distribution for those visits with monotone missing values will be equal to those means estimated for the placebo group for the same visits. The visit of interest will be subject to multiple imputation based on this distribution. This will result in multiple imputed datasets at this visit of interest. Intermittent missing values will be imputed under MAR. Participants in the placebo group with missing values at this

- visit of interest will be imputed based on the MAR assumption. The number of imputation (R) can be specified as 100 here.
- 4. For each of the R completed imputed dataset for a visit of interest, an analysis of covariance (ANCOVA) model which includes fixed effects of treatment group, actual stratification factor (ie, baseline IGA of 3 or 4 from clinical database), and baseline value, will be used to analyze the data (observed and imputed) at the visit of interest. This will generate LSM (SE) for each treatment group and LSM treatment difference estimate as well as standard error of this estimate. This will produce R sets of estimates and standard errors. These R sets of results will be combined using the Rubin's rules (Rubin 1987) to generate the combined LSM (SE) for each treatment group and LSM treatment difference estimate and its standard error, 95% CI and 2-sided p-value, for this visit of interest.

The implementation of this JTC method for continuous endpoint measured at multiple post-baseline visits under the Estimand E2 will provide analysis result for each visit of interest. The implementation may be using the Statistical Analysis System (SAS) macro developed by Carpenter, Roger and Kenward, 2013. Further programming details of JTC method will be laid out in the programming plan.

5.2.2.2. Analyses for Continuous Data (Repeated Measures With No Estimand)

When Estimand E2a or no estimand is defined for a continuous efficacy endpoint, repeated measures data for continuous endpoints will be analyzed as change or percent change from baseline as appropriate with a MMRM that includes fixed effects of treatment group, visit, treatment group-by-visit interaction, actual stratification factor (ie, baseline IGA of 3 or 4 from clinical database), actual-stratification-factor-by-visit interaction, baseline value, and baseline-value-by-visit interaction. This MMRM is similar to the estimation model used in JTC method (Section 5.2.2.1). MMRM will include observed values without imputation of missing values. A common unstructured variance-covariance matrix will be used, provided the model converges, otherwise alternative covariance structures will be attempted in this order depending on model convergence and feasibility: heterogeneous compound symmetry (CSH) then compound symmetry (CS). The Kenward-Roger degrees of freedom approximation will be used. Comparison of treatment groups (providing LSM of the treatments, LSM of the treatment difference, 2-sided p-value and 95% CI) at each included timepoint will be generated using this MMRM. MMRM can only include participants with observed baseline value and at least one observed post-baseline value. If the baseline value is missing or if there are no post-baseline measurements, this participant will not be included this analysis (Section 4.1). Therefore, when reporting the result of MMRM, the number of participants by treatment group in the FAS (N), the number of participants by treatment group included in the MMRM (N1) and the number of participants by treatment group evaluable at each of the timpoints (N2) are to be reported.

5.3. Methods to Manage Missing Data

In Part 1 DB phase, after accounting for relevant intercurrent events in the data sets (Section 2.2, Appendix 3) and visit windowing (Appendix 2.1) in the data, if a binary efficacy endpoint at a visit has missing value, it will be handled by setting the missing binary efficacy DMB02-GSOP-RF02 7.0 Statistical Analysis Plan Template 31-Jan-2022

endpoint to non-response. This method of handling missing binary efficacy endpoint is known as missing response as non-response (MR=NR). In general, if a continuous efficacy endpoint at a visit has missing value, it will remain missing and no imputation of this missing value will be performed in the datasets.

Under Estimand E1 (eg, IGA response at Week 16), after accounting for the occurrence of relevant intercurrent events in the dataset and in the FAS, missing binary efficacy endpoint at a visit will be set to non-response (ie, treatment failure). If intercurrent events have not occurred before a visit, and the binary efficacy endpoint at this visit has missing value, it will be set to non-response due to MR=NR. Under the Estimand E1a, since intercurrent events are not considered, if the binary efficacy endpoint at a visit has missing value, it will be set to non-response due to MR=NR.

For continuous efficacy endpoint analyzed under Estimand E2 (eg, percent change from baseline in EASI score at a visit), after accounting for the occurrence of relevant intercurrent events, the post-intercurrent-event data will be treated as missing, only pre-intercurrent event data will be included in the JTC method via multiple imputations (Section 5.2.2.1).

In Part 1 OLE phase, since no estimands are defined for (binary or continuous) efficacy endpoints, all observed data collected/assessed regardless of any prior intercurrent events will be included in deriving the efficacy endpoints at a visit. If the binary efficacy endpoint at any visit has missing value, it will be handled by setting the binary efficacy endpoint to non-response. This method of handling missing binary efficacy endpoint is known as missing response as non-response (MR=NR), which is similar to using Estimand E1a (treatment policy estimand). If the continuous efficacy endpoint at any visit has missing, it will remain as missing, without imputation of missing value at this visit, which is similar to using Estimand E2a (treatment policy estimand). The same approach of including all observed data collected/assessed regardless of any prior intercurrent events will also be applicable to Part 2 OL Safety phase. Missing binary efficacy endpoints in Part 2 OL Safety phase will not be imputed as non-response, only observed values will be summarized.

In general, missing values in any (binary or continuous) efficacy endpoint will not be imputed when summarizing these endpoints using descriptive statistics. In addition, missing values for safety endpoints will not be imputed.

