4.1. Full Analysis Sets

The full analysis set (FAS) will include all participants who are randomized to the study irrespective of whether they receive any dose of study intervention (ie, etrasimod or placebo). Participants will be analyzed in the treatment groups as they are randomized. If a participant DMB02-GSOP-RF02 7.0 Statistical Analysis Plan Template 31-Jan-2022

is treated but not randomized, then this participant will be excluded from the FAS. A narrative will be provided for this participant in the clinical study report (CSR). For a participant who is randomized but not treated, for Part 1 DB and OLE, baseline value for efficacy and safety endpoints is defined as the value obtained on the date of randomization as Day 1 or prior (if the Day 1 value is not available) in the Part 1 DB phase in the analyses.

In general, the analysis population for analyzing all efficacy endpoints in this study is defined by the complete FAS. However, there are some exceptions: some efficacy endpoints, defined by specific point reduction from baseline, require the inclusion of only participants who meet a baseline threshold in the analysis set to allow them the potential to respond in these efficacy endpoints. The details of these exceptions are provided below. Therefore, when considering analyzing an efficacy endpoint under an estimand, it is important to consider these exceptions.

FAS for Specific Efficacy Endpoints

The following four binary efficacy endpoints will only be analyzed including participants who meet the specific baseline threshold. This is to ensure that only participants with the potential to respond at a post-baseline visit are included in the analyses.

- IGA response defined as clear (0) or almost clear (1) on a 5-point scale and a reduction of ≥2 points from baseline (Appendix 2.2.1): Only participants with baseline IGA ≥2 in the FAS are included in all analyses of IGA response, knowing that only participants with baseline IGA ≥3 are eligible to enroll in this study.
- ≥4-point reduction in PP-NRS score from baseline (Appendix 2.2.4): Only participants with baseline PP-NRS ≥4 in the FAS are included in all analyses of this endpoint.
- ≥4-point reduction in Skin Pain NRS score from baseline (Appendix 2.2.5): Only participants with baseline Skin Pain NRS ≥4 in the FAS are included in all analyses of this endpoint.

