5. GENERAL METHODOLOGY AND CONVENTIONS

For Part 1, there will be a total of 2 planned analyses. The first (interim) analysis (IA) for Part 1 will be conducted when all applicable participants have completed or discontinued from study prior to their Part 1 DB Week 16 visit. The IA will be performed by the Sponsor and it will include all efficacy and safety data through Week 16. Data summaries from the IA will be shared with the study team. The study team will review the data in the context of the overall benefit-risk profile of etrasimod for the treatment of moderate-to-severe AD with prior systemic failure. The efficacy and safety data up to Week 16 will be utilized to assess the primary efficacy endpoint, secondary efficacy endpoints, and safety endpoints (Section 2.2, Section 5.1) and to make a go/no-go decision for initiating Part 2 of the study, as well as for completing the 52-week treatment for the Part 1 participants in the OLE. The IA efficacy results through Week 16 for Part 1 DB phase is not final and definitive.

The second (final) analysis for Part 1 will be conducted when all applicable participants have completed or discontinued from study prior to their Week 68 visit (including safety follow-up visits at Weeks 70 and 72) if Part 1 OLE is planned for completion by the sponsor. Otherwise, if Part 1 OLE is decided to be terminated by the sponsor, the final analysis will only be conducted based on data collected up to the date of study termination. The final analysis will contain final safety and efficacy data, as Part 1 final database, to assess the primary endpoints, secondary endpoints as well as exploratory efficacy endpoints (Section 2.2). This will also include efficacy analyses for Part 1 DB phase repeated based on this final data, and this final analysis is considered final and definitive.

For Part 2, there will only be one final analysis when all applicable participants have completed their Part 2 OL Safety phase Week 52 visit (including safety follow-up visits at Weeks 54 and 56) if Part 2 OL Safety phase is planned by the sponsor based on the Part 1 DB IA result. The final analysis will contain final safety data to assess the primary safety endpoints, and final efficacy data to assess exploratory efficacy endpoints (Section 2.2).

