1) Week 16 Completers with Observed Non-Response	xx (xx.xx)	xx (xx.xx)	
2) Week 16 Completers with Missing Response Set as Non-Response	xx (xx.xx)	xx (xx.xx)	
3) Initiation of Prohibited Medications Prior to Week 16 Visit (Earlier)	xx (xx.xx)	xx (xx.xx)	
4) Discontinued Study Treatment Due to Any Reason Prior to Week 16 Visit (Earlier)	xx (xx.xx)	xx (xx.xx)	
Reasons for Discontinuation of Study Treatment [2]			
Lack of Efficacy	xx (xx.xx)	xx (xx.xx)	
Adverse Event	xx (xx.xx)	xx (xx.xx)	
Death	xx (xx.xx)	xx (xx.xx)	
Lost to Follow-up	xx (xx.xx)	xx (xx.xx)	
Withdrawal by Subject	xx (xx.xx)	xx (xx.xx)	
Non-Compliance with Study Drug	xx (xx.xx)	xx (xx.xx)	
Protocol Deviation	xx (xx.xx)	xx (xx.xx)	
Pregnancy	xx (xx.xx)	xx (xx.xx)	
Physician Decision	xx (xx.xx)	xx (xx.xx)	
Medication Error without Associated Adverse	xx (xx.xx)	xx (xx.xx)	
Event			
Study Terminated by Sponsor	xx (xx.xx)	xx (xx.xx)	
Other	xx (xx.xx)	xx (xx.xx)	

^[1] N = number of participants in the FAS with Baseline IGA \geq 2. IGA response rates are calculated based on this as denominator.

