6.2.4. Other Exploratory Binary Endpoints

For Part 1 OLE, binary exploratory endpoints at all visits from Week 20 up to Week 68 (eg, EASI-75 response), will be analyzed at each visit, including all available data on the FAS (since intercurrent events are not considered in this Part 1 OLE phase), using the normal approximation for the difference in binomial proportions adjusting for the actual stratification factor of baseline IGA (3 vs 4) via the CMH approach (Section 5.2.1.1). The baseline IGA from the clinical database will be used as the actual stratification factor (Section 3.4.1). This CMH approach will provide treatment comparison of Etrasimod 2 mg QD versus Placebo → Etrasimod 2 mg QD and generate 95% CI for the EASI-75 response rate difference at this visit along with the 2-sided p-value (Section 5.2.1.1). Missing values will be handled by setting the EASI-75 response value to non-response, MR=NR (Section 5.3).

This CMH approach will also be applied to IGA of clear (0) or almost clear (1) response, \geq 4-point reduction from baseline in PP-NRS score (analyzed only for participants with baseline PP-NRS \geq 4), \geq 4-point reduction from baseline in Skin Pain NRS score (analyzed only for participants with baseline Skin Pain NRS \geq 4), and EASI-90 response, at all visits from Week 20 up to Week 68.

For Part 2 OL Safety, binary exploratory endpoints at all visits will only be descriptively summarized for the single treatment group of Etrasimod 2 mg QD using only observed values on the FAS (since intercurrent events are not considered in this Part 2 OL Safety phase). Therefore, missing responses will not be imputed using the MR=NR in this Part 2 OL Safety phase (Section 5.3). This approach is applicable to EASI-75 response, IGA of clear (0) or almost clear (1) response, \geq 4-point reduction from baseline in PP-NRS score (analyzed only for participants with baseline PP-NRS \geq 4), \geq 4-point reduction from baseline in Skin Pain NRS score (analyzed only for participants with baseline Skin Pain NRS \geq 4), and EASI-90 response, at all visits from Week 4 to Week 52. The baseline is the pre-dose Day 1 of Part 2 OL Safety phase (Section 3.4).

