7. INTERIM ANALYSES

An interim analysis (IA) will be conducted by the Sponsor in an unblinded manner to assess efficacy and safety after all applicable Part 1 participants complete or discontinue from study prior to the 16-week DB treatment period. The IA results will be used for decisions regarding stopping for futility and internal program development. Study conduct, including Part 1 participant continuation in OLE, will continue while the data are prepared and analyzed for the IA. The Part 2 enrollment will not be triggered until after IA shows an acceptable safety and efficacy of etrasimod 2 mg QD in the target population. Based on the IA results, the study may continue, or the study may be terminated early.

Specifically, the scope of this IA includes the following. When all applicable Part 1 participants have completed the 16-week DB treatment phase, an interim datacut will be performed that will include all efficacy and safety data up to Week 16 visit. After data cleaning is performed, unblinding of Part 1 DB treatment assignments will take place, and interim database will be released for the IA to be performed by the Sponsor and the study team. Investigators and other site staff will remain blinded during the OLE to participants' treatment assignment received in the Part 1 DB phase until the end of Part 1 OLE. Efficacy data summary will include the assessment of primary efficacy endpoint, secondary efficacy endpoints, and exploratory efficacy endpoints for Part 1 DB (Section 2.2) using the prespecified statistical methodologies (Section 5) to perform all relevant analyses described for Part 1 DB including subgroup analysis (Section 6.3). Safety data summary will include the assessment of all relevant safety endpoints (Section 3.5) descriptively summarized up to end of Part 1 DB phase.

Prior to this formal Part 1 DB IA, Sponsor may perform earlier unblinded interim analyses to inform internal decision-making regarding the development program. These earlier interim analyses will be conducted and reviewed by a limited number of team members independent of the study team. Details on these earlier unblinded interim analyses will be described in an unblinding operational plan.

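### If the sponsor stops the Part 1 OLE after the interim analysis, the missing-as-non-response rule counts visits not reached because of the stop as failures in the CMH-based OLE response analyses

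*SAP*

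**What the plan says.** **The rule.** For the OLE, SAP 5.3 says of a missing binary endpoint: "If the binary efficacy endpoint at any visit has missing value, it will be handled by setting the binary efficacy endpoint to non-response". SAP 6.2.4 uses the rule in a stratified CMH comparison of the two sequences (etrasimod throughout, and placebo then etrasimod). It says that EASI-75 from Week 20 to Week 68 "will be analyzed at each visit, including all available data on the FAS". The same approach covers IGA 0/1, EASI-90 and the two NRS responses; the NRS responses are restricted to participants with baseline scores of at least 4.

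**The denominator.** SAP 4.1 defines the full analysis set (FAS) as "all participants who are randomized to the study irrespective of whether they receive any dose of study intervention".

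**The stop.** SAP 2.3 and 5 use the interim analysis (IA) to decide whether Part 1 participants complete the OLE. SAP 7 adds: "Based on the IA results, the study may continue, or the study may be terminated early". It also says: "Study conduct, including Part 1 participant continuation in OLE, will continue while the data are prepared and analyzed for the IA". If the OLE is ended, SAP 5 provides that "the final analysis will only be conducted based on data collected up to the date of study termination".

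**What is treated differently.** Descriptive summaries are not imputed and use evaluable participants as denominators (SAP 5.2, 5.3). OLE continuous endpoints are analysed by MMRM without imputation (SAP 5.2.2.2, 6.2.5). Part 2 binary endpoints use observed values only (SAP 5.3, 6.2.4).

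**The concern.** Setting missing values to non-response is defensible when missingness may reflect the participant's course, such as withdrawal or discontinuation at Week 32 for not reaching EASI-50. A sponsor's decision to close the OLE is different: whether a participant had reached Week 52 by then depends mainly on when he or she was randomised. Dosing continues while the IA is prepared, so with staggered enrolment participants will be at different OLE visits when a stop is decided.

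As written, every unreached visit enters the CMH analysis as a failure and counts in the sample size. Response would seem to fade over time because of the calendar alone. EASI-75 could fall steeply while percent change in EASI, from the same participants and visits, did not. The sequence difference, its interval and its p-value exist only in the imputed form, so the descriptive table cannot replace them.

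**Working it through.** **1. The plan's own figure.** The documents give no number for OLE response or for a terminated OLE. The only design figures are in protocol 9.5: 30 per group, Week 16 IGA response of 39% and 9%, half-widths of at most 17.5% per group and 20.2% for the difference. With the unpooled normal approximation:

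- etrasimod: 1.96 × √(0.39 × 0.61 / 30) = 17.45%
- placebo: 1.96 × √(0.09 × 0.91 / 30) = 10.24%
- difference: 1.96 × √(0.39 × 0.61 / 30 + 0.09 × 0.91 / 30) = 20.24%

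These match the plan.

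**2. Effect on a rate.** Let p be the true OLE rate and r the fraction of the FAS with data at the visit. When data are absent only because of the stop, the reported rate is r × p. Assume p = 39%, borrowed from the Week 16 assumption:

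- r = 0.75: 29.2%
- r = 0.50: 19.5%
- r = 0.25: 9.8%
- r = 0: 0%

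**3. Effect on a difference.** Assume true OLE rates of 39% and 30%, the same r in both sequences, 30 per group and no stratification. The true difference is 9 points, with half-width 23.9 points when everyone has data.

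| r | Reported difference | Reported half-width |
|---|---|---|
| 0.75 | 6.75 | 22.1 |
| 0.50 | 4.5 | 19.1 |
| 0.25 | 2.25 | 14.2 |

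The interval narrows as information is lost. At r = 0.50 the 15 participants per group with data support 1.96 × √(0.39 × 0.61 / 15 + 0.30 × 0.70 / 15) = 33.9 points, not 19.1.

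**4. Which visits.** Assume uniform accrual over A weeks, a stop L weeks after the last Week 16 visit, and all participants still in the OLE. Then r(w) = min(1, max(0, 1 − (w − 16 − L)/A)). SAP Appendix 2.1 lets early termination (ET) assessments fill a window, and windows open before the target day: Week 32 at Day 197, Week 40 at Day 253, Week 52 at Day 323, Week 68 at Day 421. If everyone stopped inside a window has an ET value, w becomes (opening day − 1)/7, that is 28, 36, 46 and 60. For A = 52, L = 8 and p = 39%:

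| Visit | r, target day | Rate | r, with ET in window | Rate |
|---|---|---|---|---|
| Week 32 | 0.85 | 33.0% | 48/52 = 0.92 | 36.0% |
| Week 40 | 0.69 | 27.0% | 40/52 = 0.77 | 30.0% |
| Week 52 | 0.46 | 18.0% | 30/52 = 0.58 | 22.5% |
| Week 68 | 0.15 | 6.0% | 16/52 = 0.31 | 12.0% |

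ET data reduce the bias but do not remove it. On target days, A = 26 and L = 8 gives 27.0%, 15.0%, 0% and 0% at these four visits; A = 78 and L = 16 gives 39%, 35.0%, 29.0% and 21.0%. Weeks 20 and 24 stay at 39% in all six combinations tried (A = 26, 52, 78; L = 8, 16).

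**The case against.** **Descriptive rates already avoid the problem.** This is correct, and it limits the point. A reader might infer that all later OLE response rates are biased; they are not. Descriptive rates keep evaluable denominators and show how many participants contributed, and visits that everyone reached are untouched. What remains is that one visit would carry two conflicting rates, and the between-sequence comparison would have only the biased one.

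**SAP 5 limits the analysis to data up to termination.** One could read that as dropping unreached visits. It does not say so: it limits which data are used, whereas the rule acts on values that do not exist.

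**The primary result.** Estimand E1 counts discontinuation for any reason as failure, and Table 4 of SAP 6.1.2 lists "Study Terminated by Sponsor" among the reasons, so a reader might infer that a stop damages the Week 16 analysis. The documents do not support that for a stop after the formal IA, which takes place once participants have completed or left the double-blind phase. Table 4 also already shows sponsor termination as a separate row.

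**Visits nobody reached.** With 0% in both groups and both strata, SAP 5.2.1.1 performs no formal comparison. That is true, but the 0% would still be reported as observed.

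**Importance.** OLE efficacy is exploratory, has no estimand, and comes after the go/no-go decision. This stands and keeps the point modest.

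**Conclusion.** The point holds within limits. If the sponsor ends the OLE after the IA, the CMH-based OLE response rates are biased downward in proportion to the share of the FAS without data, sequence differences shrink toward zero, and intervals are too narrow. This applies only at visits that some participants had not reached and for which they have no value in the window. At r = 0.50, 39% becomes 19.5%, and a 9-point difference becomes 4.5 with a half-width of 19.1 instead of 33.9 points.

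The direction follows from the SAP's text. The sizes rest on assumed response rates, accrual and stopping times, none of which the documents give for the OLE, and on equal reach in both sequences. The descriptive OLE rates, the OLE continuous endpoints, the go/no-go decision and the Week 16 primary analysis are unaffected. The change should be made, but the study's main conclusion does not depend on it.

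**What to change.** Add to SAP 5.3 and 6.2.4, for the case where the sponsor terminates the OLE:

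- Missing is set to non-response at an OLE visit only if the participant's scheduled date for that visit, projected from Day 1 whether or not he or she had already discontinued, falls on or before the termination date.
- Any value observed in the analysis window, including ET data, is kept. A cut-off on target day alone would discard real observations: a participant stopped at Day 330 with an ET assessment has a Week 52 value although the target is Day 365.
- The CMH denominator at each visit is FAS participants with an observed value or with the visit due by the termination date, and it is reported.
- Non-response still applies to withdrawals, participants who never entered the OLE and Week 32 EASI-50 discontinuations, where the visit was due.

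The cost is a short SAP amendment and a derived visit-due flag, with smaller denominators and wider intervals at late visits. ET values kept ahead of the due date come from participants still under observation at the stop, so their number should be shown beside the denominator. The change should be made before unblinding for the IA, so that the rule is not chosen with results in hand.
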